6.2 Sample Size, Accrual Rate and Study Duration

The sample size was calculated based on the data by Rhodus et al., as to ensure at least 80% power and two-sided alpha of 0.05 in detecting a t difference of 2.0 points oral pain on an 11 point scale (VAS 0-10) between Arm A and B²⁴. The mean expected change for Arm A will be 6.5 points reduction with a standard deviation of 1.4 points. The mean expected change for Arm B will be 4.5 points reduction with a standard deviation of 1.4 points.

A total of 12 patients per arm will be enrolled (total of 24 subjects). The proposed sample size includes a loss of follow up of 5%. Approximately 75 patients per year are diagnosed with oral lichen planus at the Division of Oral Medicine and Dentistry (BWH)³². We anticipate the accrual rate will be approximately 5 patients per month, thus the accrual goal will be achieved in approximately five months.

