6.5 Analysis of Secondary Endpoints

Oral health related quality of life will be assessed before and after topical therapy using the 24-item Chronic Oral Mucosal Diseases Quality of Life Questionnaire (COMDQLQ; see Appendix) instrument that measures subject's perceptions of the impact of oral conditions on their well-being. The COMDQLQ scores will be summarized descriptively for each arm at pre-treatment, post-treatment, and pre-to-post treatment change. The pre-to-post treatment change for each item and for all items combined will be assessed within each arm using either paired t test or Wilcoxon-signed-rank test depending on its distribution. In addition, each question will be dichotomized and classified as 'response' if the answer is 'not at all', or 'slightly' to a question such as "how isolated do you feel as a

CONFIDENTIAL

This document is confidential. Do not disclose or use except as authorized.

result of this oral condition”, and pre-to-post treatment improvement will be assessed using McNemar’s test within each arm.

In order to evaluate the clinical improvement in clinician-reported outcome measures for oral lichen planus, REU scores within the compound dexamethasone solution in Mucolox™ group (Arm A) will be compared to that in the dexamethasone solution only group (Arm B). The REU scores will be summarized descriptively for each arm at pre-treatment, post-treatment, and pre-to-post treatment change. The pre-to-post treatment change will be compared between the arms using either student’s t-test or Mann–Whitney test, depending on the distribution of the data.

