8. Rate the taste of the topical treatment:

[figure not shown]
[figure not shown]

Very good taste

Very bad taste

Score: _____

9. Rate how your mouth feels since starting topical therapy:

Mouth feels much better

Mouth feels much worse

Score: _____

10. Overall, since beginning topical therapy, my mouth is: (Check one)

- Very much better
- Moderately better
- A little better
- About the same
- A little worse
- Moderately worse
- Very much worse

CONFIDENTIAL

This document is confidential. Do not disclose or use except as authorized.

OBJECTIVE DATA

Site	Reticular area			Erythematous area			Ulcerative area			
	0	1	0	1	2	3	0	1	2	3
Upper/lower labial mucosa	0	1	0	1	2	3	0	1	2	3
Right buccal mucosa	0	1	0	1	2	3	0	1	2	3
Left buccal mucosa	0	1	0	1	2	3	0	1	2	3
Dorsal tongue	0	1	0	1	2	3	0	1	2	3
Ventral tongue	0	1	0	1	2	3	0	1	2	3
Floor of mouth	0	1	0	1	2	3	0	1	2	3
Hard palate mucosa	0	1	0	1	2	3	0	1	2	3
Soft palate/tonsillar pillars	0	1	0	1	2	3	0	1	2	3
Maxillary gingiva	0	1	0	1	2	3	0	1	2	3
Mandibular gingiva	0	1	0	1	2	3	0	1	2	3
Total										

(R: 0 = not present, 1 = present; E & U: 0 = not present, 1 = <1cm², 2 = 1 - 3cm², 3 = >3cm²)

Total Score:

Total Weighted Score:

PHOTOGRAPHS TAKEN (circle): YES NO

CONFIDENTIAL

This document is confidential. Do not disclose or use except as authorized.

COMDQLQ

	Not at all (0)	Slightly (1)	Moderately (2)	Considerably (3)	Extremely (4)
Pain and functional limitation					
How much do certain types of food/drink cause you discomfort (spicy food, acidic food)?					
How much does your oral condition cause you to limit the types of food/ drinks you consume?					
How much do certain food textures cause you discomfort (rough food, crusty food)?					
How much does your oral condition cause you to limit the textures of the food you consume?					
How much does the temperature of certain foods/drinks cause you discomfort?					
How much does your oral condition cause you to limit the temperature of the foods/ drinks you consume?					
How much does your oral condition lead to discomfort when carrying out your daily oral hygiene routine (brushing, flossing, mouthwash usage)?					
How much does your oral condition cause you to limit your daily oral hygiene routine (brushing, flossing, mouthwash usage)?					
How much does your oral condition lead to discomfort when wearing a denture (false teeth)?					
Medication and treatment					

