How much do you feel you need medication to help you with activities of daily life (talking, eating, etc.)?					
How satisfied are you with the medication being used to treat your oral condition?					
How concerned are you about the possible side effects of the medications used to treat your oral condition?					
How much does it frustrate you					

CONFIDENTIAL

This document is confidential. Do not disclose or use except as authorized.

that there is no single standard medication to be used in your oral condition?					
How much does the use of the medication limit you in your everyday life (routine/the way you apply or take your medications)?					
How much does it bother you that there is no cure for your oral condition?					
Social and emotional					
How much does your oral condition you down?					
How much does your oral condition cause you anxiety?					
How much does your oral condition cause you stress?					
How much does the unpredictability your oral condition bother you?					
How much does your oral condition cause you to worry about the future (spread of the condition, possible cancer risk)?					
How much does your oral condition make you pessimistic about the future?					
How much does your oral condition disrupt social activities in your life (social gatherings, eating out parties)?					
Patient support					
How satisfactory do you consider the information available to you regarding your oral condition?					
How satisfied are you with the level of support and understanding shown to you by family regarding this oral condition?					
How satisfied are you with the level of support and understanding shown to you by friends/work colleagues regarding your oral condition?					
How isolated do you feel as a result of this oral condition?					

CONFIDENTIAL

This document is confidential. Do not disclose or use except as authorized.

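### Section 6.5 plans about 100 unadjusted within-arm tests of single COMDQLQ items in arms of 12, with no lead result; at least one chance finding is likely if nothing truly changes

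*Combined protocol and SAP*

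**What the plan says.** Section 6.5 (Analysis of Secondary Endpoints) first summarises COMDQLQ scores descriptively by arm. It then tests them: "The pre-to-post treatment change for each item and for all items combined will be assessed within each arm using either paired t test" or the Wilcoxon signed-rank test, depending on the distribution.

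A second layer follows on the same answers: "In addition, each question will be dichotomized and classified as" a response when the answer is one of the two lowest levels, and "pre-to-post treatment improvement will be assessed using" McNemar's test within each arm. The version of McNemar's test (exact, uncorrected or continuity-corrected) is not given.

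The section states no significance level, no multiplicity adjustment, no lead COMDQLQ result and no exploratory label for the item tests. A two-sided 0.05 appears only in section 6.2, for the primary endpoint. The other secondary endpoint, the REU score, has a single between-arm comparison of change.

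Sections 5.1.2 and 6.5 describe a 24-item instrument. The form in Appendix 5 prints 26 rows under four headings, among them "Pain and functional limitation" and "Social and emotional". It prints no domain scores and no scoring rule.

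**The concern.** Quality of life is one of two secondary objectives (section 2.3). The plan answers it with about 100 p-values and no statement of which one is the answer. Single five-level items in 12 patients are the noisiest level at which the instrument can be read, and each is tested twice. The McNemar step reuses the answers already in the paired test after discarding most of their information.

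Two things are at stake. A reader of the results could not tell items that truly improved from items that crossed 0.05 by chance. And where the exact and uncorrected McNemar tests disagree, the result would turn on a choice that the plan leaves open.

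**Working it through.** **Inputs.** Patients per arm: 12 (section 6.2). Items: 24 (sections 5.1.2 and 6.5) or 9 + 6 + 7 + 4 = 26 rows (Appendix 5). Level: two-sided 0.05, borrowed from section 6.2 because 6.5 gives none.

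**The plan's own figure.** The documents give no test count or error rate for 6.5. The figure that can be checked is the arm size. Section 6.2 asks for "at least 80% power and two-sided alpha of 0.05" to detect a "difference of 2.0 points oral pain on an 11 point scale (VAS 0-10) between Arm A and B", with SD 1.4. The t-test needs 9 per arm, or 10 after 5% loss. Dividing the unrounded t-test size (8.76) by the Mann-Whitney worst-case efficiency of 0.864 gives 11, or 12 after loss, which matches. So 12 per arm is sound for the primary endpoint. It was not derived for item-level tests.

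**Test count.** Items × 2 tests × 2 arms + 2 totals:
- 24 × 2 × 2 + 2 = 98
- 26 × 2 × 2 + 2 = 106

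**McNemar at this size.** With b improved and c worsened, the uncorrected statistic is (b − c)²/(b + c).
- b = 4, c = 0: statistic 16/4 = 4, p = 0.046. Exact: 2 × 0.5⁴ = 0.125.
- Exact, five all one way: 2 × 0.5⁵ = 0.0625. Six all one way: 2 × 0.5⁶ = 0.031.

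The exact test therefore needs at least six discordant patients out of 12 to reach p < 0.05. Its simulated size was about 0.4% per test, against about 4.5% for the uncorrected version.

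**Expected false positives if no item changes.** Paired tests (items plus total, two arms) at 5%, plus McNemar tests at their simulated size:
- 24 items, exact: 50 × 0.05 + 48 × 0.004 = 2.7
- 24 items, uncorrected: 50 × 0.05 + 48 × 0.045 = 4.7
- 26 items, exact: 54 × 0.05 + 52 × 0.004 = 2.9
- 26 items, uncorrected: 54 × 0.05 + 52 × 0.045 = 5.0

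**Chance of at least one.** The tests are not independent, so this was simulated: 2,000 runs per setting, 12 complete patients per arm, five equally likely answer levels, no true change, paired t plus McNemar. The assumed pre-post correlation was 0.5. The inter-item correlation was varied because the documents give none. Each cell shows 24 / 26 items.

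| Inter-item correlation | With exact McNemar | With uncorrected McNemar |
|---|---|---|
| 0 | 91% / 93% | 97% / 98% |
| 0.3 | 86% / 89% | 96% / 97% |
| 0.5 | 77% / 80% | 92% / 93% |
| 0.7 | 65% / 66% | 84% / 87% |
| 0.9 | 44% / 45% | 65% / 67% |

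Simulated mean counts were 2.5 to 2.9 (exact) and 4.4 to 5.2 (uncorrected). The exact McNemar tests add almost nothing: with 24 items at correlation 0.5 the chance is 77.2% with them and 76.5% without.

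**After the change.** If only the total is tested, within each arm as 6.5 now has it, two tests remain on separate patients. Expected false positives are 2 × 0.05 = 0.1, and the chance of at least one is 1 − 0.95² = 9.75%.

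**The case against.** The strongest reply is that the no-change premise does not fit this trial. Both arms receive active treatment (section 9.1), entry requires a worst sensitivity of at least 7 (section 3.1), and section 6.2 expects large falls: "The mean expected change for Arm A will be 6.5 points reduction with a standard deviation of 1.4 points", and 4.5 points for Arm B. Nine of the printed rows concern pain and function. Many within-arm changes may be real, and a test of an item that truly changes cannot be a false positive. This stands as a limit on the figures. It does not supply a way to separate real from chance findings among about 100 unranked tests.

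A second reply is context: a 24-patient, open-label phase II trial with one primary endpoint and no decision tied to any COMDQLQ p-value. That is a fair argument against demanding formal error control for every item. It does not argue against naming one result and labelling the rest.

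Three stronger readings are tempting but not supported:
- A reader might infer that a chance finding is near certain. That needs nearly independent items or the uncorrected McNemar test. With the exact version and correlations of 0.5 to 0.7 the chance is 65% to 80%.
- A reader might infer that established domain scores are being ignored. Appendix 5 prints headings only. Whether validated domain scores exist depends on a source outside the documents.
- A reader might infer that the plan permits selective reporting. Section 6.5 prespecifies every item and the combined score. What it lacks is a ranking among them.

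**Conclusion.** The point holds. Section 6.5 plans 98 to 106 unadjusted within-arm COMDQLQ tests in arms of 12, two per item on the same answers, with no lead result and no exploratory label. If nothing truly changed, about 2.5 to 5 would be false positives. At least one is likely: roughly 65% to 98% for inter-item correlations of 0 to 0.7, and still 44% to 67% at 0.9.

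These figures assume a two-sided 0.05 per test, complete data, a pre-post correlation of 0.5 and equal correlation among items. They apply only to items with no true change. The dependence on the McNemar version needs no such assumption: 4 versus 0 gives 0.046 or 0.125.

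This should be corrected, but it leaves the primary analysis untouched. The absence of a between-arm COMDQLQ comparison is a separate matter and is not judged here.

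**What to change.** In section 6.5, before outcome data are examined:

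1. Name the COMDQLQ total, already planned as the combined score, as the one tested quality-of-life result.
2. First reconcile the 24 items in the text with the 26 rows on the form, so that it is clear what is summed. Four rows ask about satisfaction (one on medication, one on information, two on support), where a higher answer is better. Reverse-score them so that the total has one direction.
3. Report single items descriptively without p-values, or label their tests exploratory. Sums under the four printed headings may be shown on the same terms.
4. Delete the item-level McNemar tests. If any are kept, specify the exact version.

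Adjusting across all items is not a usable alternative. Bonferroni would need p < 0.05/98 = 0.00051 or 0.05/106 = 0.00047, while the smallest exact McNemar p-value with 12 patients is 2 × 0.5¹² = 0.00049, reached only if all 12 change the same way.

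The cost is revised wording in 6.5 and a short scoring rule. No patients, visits or data are added. The downside is the loss of item-level p-values, which 12 patients per arm cannot support.

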6.4 Analysis of Primary Endpoints

VAS scores will be summarized descriptively for each arm at pre-treatment, post-treatment, and pre-to-post treatment change. The pre-to-post treatment change will be compared between the arms using either Student's t-test or Mann-Whitney test, depending on the distribution of the data.

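### The COMDQLQ response rule in Section 6.5 runs backwards, or is missing, for four satisfaction items, and no between-arm COMDQLQ comparison is planned

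*Combined protocol and SAP*

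**What the plan says.** **Response rule.** Section 6.5 adds a dichotomised analysis of the COMDQLQ: "each question will be dichotomized and classified as 'response' if the answer is 'not at all', or 'slightly' to a question such as" the isolation item, which is a burden item and the only example. Pre-to-post improvement is then tested by McNemar's test within each arm.

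**Form.** Appendix 5 uses one response header for all items, *not at all* (0) to *extremely* (4), and marks no item as reversed. Four items are worded positively:
- on medication: "How satisfied are you with the medication being used to treat your oral condition"
- an item on whether the patient finds the available information satisfactory
- on family support: "How satisfied are you with the level of support and understanding shown to you by family regarding this oral condition"
- the matching item on support from friends or work colleagues.

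**Analysis of change.** Section 6.5 states: "The COMDQLQ scores will be summarized descriptively for each arm at pre-treatment, post-treatment, and pre-to-post treatment change". It continues: "The pre-to-post treatment change for each item and for all items combined will be assessed within each arm", by paired t-test or Wilcoxon signed-rank test. For VAS, Section 6.4 says: "The pre-to-post treatment change will be compared between the arms using either" a t-test or Mann-Whitney test. Section 6.5 gives the same between-arm comparison for REU.

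**Item count.** Sections 5.1.2, 6.1 and 6.5 describe a 24-item instrument.

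**The concern.** A cut at the low end of the scale marks a good outcome only for burden items. On a satisfaction item it marks a bad one. A patient who moves from *not at all* to *extremely* satisfied with the medication would be recorded as losing response, and enough such patients would give a significant worsening. The combined score has a related gap: no reversal is stated, so gains in satisfaction could offset falls in burden.

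The missing contrast is a separate matter. The trial randomises in order to isolate the vehicle, and the hypothesis in Section 2.4 is comparative. Both arms receive active steroid (Section 9.1), so improvement within each arm is expected whether or not Mucolox adds anything. If one arm reaches significance and the other does not, a reader may take that as a vehicle effect; if both do, a real difference stays hidden.

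**Working it through.** **1. Count the items (Appendix 5).** Pain and functional limitation 9, medication and treatment 6, social and emotional 7, patient support 4: 9 + 6 + 7 + 4 = 26 printed, against 24 stated. Four are satisfaction items (one under medication, three under support), leaving 26 − 4 = 22 burden items.

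**2. Apply the rule to a satisfaction item.**

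| Reading of Section 6.5 | *Not at all* satisfied | *Extremely* satisfied |
|---|---|---|
| Literal (each question) | response | no response |
| Narrow (only questions like the example) | no rule | no rule |

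Neither reading gives a usable definition.

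**3. When would a false worsening be declared?** Exact two-sided McNemar, from the binomial with probability 0.5 on the discordant pairs:
- 5 versus 0: 2 × 0.5^5 = 0.063
- 6 versus 0: 2 × 0.5^6 = 0.031
- 7 versus 1: 2 × (1 + 8) × 0.5^8 = 0.070
- 8 versus 1: 2 × (1 + 9) × 0.5^9 = 0.039

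At least 6 of 12 patients would have to cross the cut, all in one direction. The medication item is the likeliest to move. Nothing in the documents suggests that a four-week rinse changes satisfaction with information or support. Criterion 3.2.1 excludes patients already on steroids, so the baseline medication answer may itself be hard to interpret.

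**4. Combined score, only if the instrument's own scoring does not reverse these items.** Let each burden item fall by one category.
- No satisfaction item moves: −22 either way, so no dilution.
- The medication item also improves by one: unreversed −22 + 1 = −21; reversed −23. Dilution 2/23 = 9%.
- All four satisfaction items improve by one: −18 against −26, or 8/26 = 31%. The documents give no reason to expect this.

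**5. What the within-arm tests can show.** The documents give no SD for COMDQLQ change, so effects below are assumed, in SD units of change. Power p is for a two-sided paired t-test at 0.05 with n = 12 (Section 6.2), from the noncentral t. With the same true change in both arms, the chance that exactly one is significant is 2p(1 − p).

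| True change in both arms | p | Exactly one arm significant |
|---|---|---|
| 0.5 SD | 0.353 | 46% |
| 0.8 SD | 0.714 | 41% |
| 1.0 SD | 0.883 | 21% |
| 1.2 SD | 0.965 | 7% |
| 1.5 SD | 0.997 | 0.6% |

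Now suppose the arms truly differ by 0.5 SD. Both are significant in 0.997 × 0.883 = 88% of trials at 1.5 versus 1.0 SD, and in 99.7% at 2.0 versus 1.5 SD. The p-values then do not reveal the difference. For scale, the only within-arm planning values in the documents are for VAS: 4.5/1.4 = 3.2 SD and 6.5/1.4 = 4.6 SD.

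**6. What a between-arm estimate would deliver.** The 95% CI half-width is t(0.975, 2n − 2) × √(2/n):
- n = 12: 2.074 × 0.408 = 0.85 SD
- n = 11 (12 × 0.95 = 11.4, rounded down): 2.086 × 0.426 = 0.89 SD

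Two-sample t-test power at 12 per arm is 22% for a 0.5 SD difference and 80% at 1.2 SD.

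**The case against.** The practical reach is small. If information and support do not move, the response rule affects one item of 26, in a supplementary analysis of a secondary endpoint, and false worsening needs at least 6 of 12 patients to cross. A sensible analyst might read the example as meaning the favourable end of the scale and mirror the cut. The instrument is cited as validated, and its scoring may already reverse these items. On the contrast, Section 2.3 names no comparator for the COMDQLQ, so within-arm analysis does not contradict that objective. No section says the two p-values will be used to claim a vehicle effect. Per-arm summaries would let a reader subtract the means, and the disagreement rates rest on assumed effects and are negligible at 1.5 SD and above.

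Much of this stands, and it limits the weight of the point. It does not remove it. The mirrored cut is written nowhere. Published scoring would not supply one, because the dichotomy is the protocol's own and acts on the answer words. Subtracting arm means is not a planned difference with an interval. Large changes in both arms do not rescue the within-arm tests: both then reach significance whatever the vehicle does.

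**Conclusion.** The point holds and should be corrected, at secondary-endpoint weight.

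- **Response rule:** wrong or undefined for 4 of 26 printed items. This follows from the text and the form alone.
- **Combined score:** not reproducible from the plan, because neither item direction nor the set of items is stated. Dilution is 0% to 9% in the plausible cases, and only if the instrument does not reverse.
- **Between-arm comparison:** no difference, interval or test is planned for the COMDQLQ, unlike VAS and REU. This is a missed randomised comparison, not a conflict with Section 2.3. The 46% to 0.6% range depends on an assumed change of 0.5 to 1.5 SD.

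The primary analysis and the REU analysis are unaffected.

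**What to change.** Amend Section 6.5 before any outcome data are seen:

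1. For the four satisfaction items, define response as *considerably* or *extremely*. Reverse-score them in the total, or cite the instrument's scoring rule if it already does so.
2. Reconcile the 24 items stated with the 26 printed, and list the items that enter the total.
3. Add a between-arm difference in COMDQLQ total change with a 95% CI, using the same t-test or Mann-Whitney rule as REU, or an ANCOVA adjusted for baseline. Present it as an estimate, not a powered test.
4. Label the within-arm and item-level tests descriptive.

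No new assessments are needed, since the COMDQLQ is already scheduled at both visits. The cost is SAP wording and a few lines of code. The drawbacks are that item-level p-values lose inferential status and that the between-arm estimate will be imprecise.
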